5.3. Withdrawal of subjects

Subjects must be withdrawn under the following circumstances:

5.3.1 The subject withdraws consent.

5.3.2 Discretion of investigator, for example:

- The investigator feels that the subject is too money motivated.
- The investigator feels that the subject does not fully comprehend and understand the consent form.
- The subject is ill-mannered and/or shows aggressive behavior towards study staff.
- Malfunction of the device for greater than 30 minutes that prevents accurate collection of optical data.
- Subject displays or communicates signs of discomfort or distress so that the study may not be continued.

5.4. Replacement of subjects

In case a subject is withdrawn from the study, another subject may be recruited.

6. EQUIPMENT AND MATERIALS

Equipment and Materials: All lab analyzers and equipment will be maintained per manufacturer specifications and all study personnel will be trained on the use of relevant equipment. Equivalent equipment and materials to those listed below may be used.

Safety Equipment (FDA-Cleared)

- Blood pressure monitoring system
- A-line pressure transducer
- Electrocardiogram (ECG)
- Masimo Pulse Oximeters (Radical-7) - for subject safety monitoring
- Pulse oximeter sensors and cables (Masimo SET, Masimo rainbow)
- Masimo Patient Monitoring Platform (Root®)- for subject safety monitoring

Oxygen Reserve Index (ORi) Validation of INVSENSOR00014

- Medical-grade Oxygen tank and mask
- Crash cart

Test Devices

- Masimo INVSENSOR00014 Rainbow sensor – Investigational

Research Equipment

Passive Data Collection Research Equipment

7. PROCEDURE

7.1 SCHEDULE OF ACTIVITIES

This figure is a 2D grid visualization. It consists of a large number of small squares arranged in a rectangular pattern. The squares are either black or white. A prominent feature is a vertical column of black squares that runs from the top to the bottom of the grid. Another prominent feature is a horizontal row of black squares that runs from the left to the right of the grid. The rest of the grid is filled with white squares. The entire grid is enclosed within a thick black border.

**Oxygen Reserve Index (ORi) Validation of
INVSENSOR00014****7.2. RECRUITMENT AND PRESCREENING**

Subjects will be recruited using IRB-approved advertisements. Subjects may be referred to the study by previous subjects. Subjects are contacted via phone call to conduct a prescreening interview to determine their initial eligibility for the study. Potential eligible subjects are scheduled for a study visit to the clinical laboratory.

7.3. CONSENTING AND SCREENING

- 7.3.1. Study staff will discuss the informed consent process and the study with the potential subjects. The subjects will be provided with enough time to read and understand the informed consent document and their questions will be answered by study staff prior to the subject signing the informed consent form. No study related activities will be conducted until consent is signed.
- 7.3.2. The subject's weight and height are self-reported, however the subject may be weighed on a scale for verification.
- 7.3.3. Subjects will be asked to provide a copy of their valid government photo ID and/or Social Security Number (SSN) card to verify subject identity. The copies of these forms of identification will be stored along with the subject's consent. The confidentiality and retention of these documents will be protected to the extent provided and required by law.
- 7.3.4. Subjects will be asked a brief series of health questions to ensure their eligibility for this study. Subjects who do not meet the inclusion and exclusion criteria will not be eligible to participate in the study.
- 7.3.5. Subject demographic information including age, sex, skin tone, ethnicity, height and weight will be collected. These may be recorded for data analysis and/or subject safety monitoring purposes.
- 7.3.6. In addition, a medical history will be recorded after the initial screening questionnaire.
- 7.3.7. Pre-procedure vital signs will be recorded for subject safety monitoring. Spikes in blood pressure and heart rate can be expected during line placement, needle sticks, blood draws etc. and may also be attributed to anxiety/nervousness relating to a new environment. Only the initial recorded blood pressure and/or heart rate determines a subject's qualification for the study.
- 7.3.8. Female subjects will be required to take a pregnancy test. Results will be noted in study documentation. If the pregnancy test is positive, the subject will be notified and removed from the study.

**Oxygen Reserve Index (ORi) Validation of
INVSENSOR00014**

- 7.3.9. A venous sample will be obtained via needle stick or by placement of an IV and analyzed to verify that the subject meets the inclusion criteria for hemoglobin level and HbCO. The subject will be excluded from the study if the values from the blood draw fall outside the ranges stated in the inclusion criteria.
- 7.3.10. Subjects may have a blanket placed on them for their comfort.
- 7.3.11. Subjects may be offered a snack (e.g., granola bar) and/or beverage (e.g., water, juice) due to the amount of time their involvement in this study may take.

7.4. PROCEDURES

- 7.4.1. Standard hospital-type monitors will be placed on the subject, including ECG, blood pressure, and a reference pulse oximeter for safety monitoring by medical staff.
- 7.4.2. Proprietary Masimo data collection software will be used to verify all oximeters are reading. If not, proper sensor positioning will be checked and sensors may be repositioned, as needed.
- 7.4.3. Rainbow parameter output values (e.g., SpO₂, pulse rate, PI) along with ORi will be recorded using the proprietary Masimo data collection software. These values match the values calculated by the instrument at runtime.
- 7.4.4. A peripheral venous line will be placed in the subject's hand or arm. This line may be used for the qualifying venous blood draw and for safety or clinical intervention required during the study.
- 7.4.5. Local anesthetics such as lidocaine, ethyl chloride spray, or Pain Ease skin refrigerant spray may be used in the event that an IV is placed to numb the site. Subjects will be given the option to have lidocaine or numbing spray be used during IV placement for the purpose of making catheter placement more comfortable for the subjects.
- 7.4.6. After intravenous access is established, one or more intra-arterial catheter(s) (arterial line or A-line) will be placed in the radial artery of the subject's wrist. The A-line is placed to facilitate continuous blood pressure measurement for subject safety monitoring, and/or to enable repeated removal of blood aliquots for reference arterial blood gases (ABG), Hgb, Hct, as well as other non-infectious blood solutes.
- 7.4.7. After arterial access is established, sensors will be placed on the required sensor sites.

Arterial blood samples will be drawn at specified targeted increments.

**Oxygen Reserve Index (ORi) Validation of
INVSENSOR00014**

Upon indication the subject is comfortable, a gas mixture will be administered. The proportion of inspired oxygen (FiO₂) will be increased in specified targeted increments

7.4.9 After reaching the desired targeted FiO₂ levels during hyper-saturation, the proportion of inspired oxygen (FiO₂) will be decreased in specified targeted increments until reaching room air; samples should be drawn at each targeted saturation level. After reaching room air, the subject may be allowed to breathe room air

After hyper-saturation and return cycle, the volunteer is desaturated until SpO₂ drops to approximately. The lowest allowable value will be oxygen saturation. Readings near will be immediately verified to ensure that levels are within the targeted oxygen saturation range and to minimize time that the subject may drop below the targeted range. Note: At any point in the study, if the subject feels uncomfortable, the subject will be given 100% oxygen

7.4.11 The study will end with several minutes at a FiO₂ greater than or equal to room air (>21%) to help the subject re-saturate after the procedures.

7.4.17 If at any point the subject is uncomfortable with the study, the study will be stopped.

7.4.18 At the conclusion of the procedure, the sensors/devices, IV(s), and arterial line(s) will be removed and the subject will be allowed to leave after medical personnel determine it is safe to do so.

7.4.19 The total procedure time will be approximately.

7.4.20 All subjects will be encouraged to remain in the study area until they feel fit to leave; subjects should feel safe and able before returning to work directly after participation in the study.

7.4.21 Subjects will be given instructions on wound care. All subjects will be instructed to contact the principal investigator or study staff in the event of any potential complication.

7.4.22 Subjects will be paid for their time.

7.4.23 Subjects will be provided with information related to any significant new findings that develop at any time during the study which may relate to their willingness to continue their participation.

Oxygen Reserve Index (ORi) Validation of INVSENSOR00014

8. ACCEPTANCE CRITERIA

For validation studies, acceptance criteria is determined by Masimo specifications for each design.

9. SAMPLE SIZE JUSTIFICATION

[REDACTED] we need 22 completed subjects for this study. The subjects should be both male and female with varying skin pigmentation.

10. DATA ANALYSIS PROCEDURE TO BE USED

Data from subjects who did not go through the full protocol are excluded from data analysis. Specificity, sensitivity and concordance will be computed for changes in ORi with respect to changes in PaO2 as described below:

ΔPaO₂ vs ΔORI

ΔPaO₂ and ΔORI are defined below.

$$\Delta\text{PaO}_2 = \text{PaO}_2(t) - \text{PaO}_2(t_{\text{ref}})$$

where t_{ref} is the time of the sample closest to $\text{PaO}_{2\text{threshold}}$ in a ± 10 mmHg (see footnote⁵) window. A ± 10 mmHg window is used as it is not possible to draw a blood sample at the exact desired value of $\text{PaO}_{2\text{threshold}}$. PaO_2 can be any value from 110 to 190 in steps of 10mmHg (see footnote) to cover the range of 100 to 200mmHg..

$$\Delta\text{ORI} = \text{ORI}(t) - \text{ORI}(t_{\text{ref}})$$

Samples with ΔPaO_2 of ± 10 mmHg are ignored (see footnote⁵).

⁵ Bedford, Robert F. MD, (1978), Long-term radial artery cannulation: effects on subsequent vessel function, *Critical Care Medicine*, 6 (1), 1-71.

⁵ Slogoff S, Keats AS, Arlund C, (1983), On the safety of radial artery cannulation, *Anesthesiology*, 59 (1), 42-47.

Oxygen Reserve Index (ORi) Validation of INVSENSOR00014

1) As per Figure 2, specificity is defined as

$$\text{Specificity} = N_1 / (N_1 + N_4)$$

2) As per Figure 2, sensitivity is defined as

$$\text{Sensitivity} = N_3 / (N_2 + N_3)$$

3) As per Figure 2, concordance is defined as

$$\text{Concordance} = (N_1 + N_3) / (N_1 + N_2 + N_3 + N_4)$$

The relationship between Concordance, Specificity and Sensitivity is as shown below.

Let $N = (N_1 + N_2 + N_3 + N_4)$

$$\begin{aligned} \text{Concordance} &= \frac{N_1}{N} + \frac{N_3}{N} \\ &= \frac{N_1 (N_1 + N_4)}{N (N_1 + N_4)} + \frac{N_3 (N_2 + N_3)}{N (N_2 + N_3)} \\ &= \frac{N_1 + N_4}{N} * \text{Specificity} + \frac{N_2 + N_3}{N} * \text{Sensitivity} \end{aligned}$$

$$\text{Concordance} = \alpha * \text{Specificity} + (1 - \alpha) * \text{Sensitivity}$$

where $0 \leq \alpha \leq 1$.

[figure not shown]

Figure 2: Specificity and Sensitivity Illustration for ΔPaO_2 vs ΔORI

Oxygen Reserve Index (ORi) Validation of INVSENSOR00014

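### Excluding every subject who did not finish the full protocol makes inclusion depend partly on device function and discards valid PaO2/ORi pairs drawn before a stop

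*Combined protocol and SAP*

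**What the plan says.** Section 10 (Data Analysis Procedure To Be Used) sets the analysis set in one sentence: "Data from subjects who did not go through the full protocol are excluded from data analysis". The readable text gives no exception, no definition of the full protocol and no supporting analysis on a wider set.

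Four other parts of the plan decide what that sentence does.

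- **Withdrawal (5.3.2).** Under "Discretion of investigator, for example", the examples include "Malfunction of the device for greater than 30 minutes that prevents accurate collection of optical data". Distress and poor comprehension of the consent form are also listed.
- **Replacement (5.4).** "In case a subject is withdrawn from the study, another subject may be recruited".
- **Sample size (9).** "we need 22 completed subjects for this study"; the reasoning behind the number is redacted.
- **Order of the procedure (7.4).** In the hyper-saturation and return cycle, "samples should be drawn at each targeted saturation level" (7.4.9). The next stage begins "After hyper-saturation and return cycle, the volunteer is desaturated until" a target that is not readable. Step 7.4.11, the described end of the study, comes after that.

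**The concern.** The outcome measures in Section 1 are sensitivity, specificity and concordance of the investigational sensor. A validation estimate should not depend on whether the device performed well enough for the subject to finish. Here it can: a long malfunction can lead to withdrawal, the subject may be replaced, and nothing measured in that subject enters the performance figures.

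The rule also acts on subjects where the analysis acts on sample pairs. A subject who stops late may already have given pairs that meet every Section 10 condition: a reference sample within 10 mmHg of a threshold, and a further sample whose change in PaO2 lies outside ±10 mmHg. All of these are dropped.

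The published figures would then describe only subjects in whom the whole procedure was completed, and the readable text does not plan to show the exclusions beside them.

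**Working it through.** **Reading the sections together**

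1. Malfunction over 30 minutes is a listed example of withdrawal (5.3.2). A withdrawn subject has not gone through the full protocol, so Section 10 excludes all of that subject's data. Device function is one of several routes to exclusion; withdrawn consent, distress and other discretionary reasons are the others.
2. Samples are taken during the rise and fall of inspired oxygen (7.4.9). Desaturation follows, then the described end (7.4.11). A subject stopped in desaturation has not reached that end but may already have supplied valid pairs. A subject stopped partway through the oxygen steps has not completed the protocol on any reading of the term, and may also have supplied some.
3. Not every stop loses pairs. A withdrawal over consent comprehension ("The investigator feels that the subject does not fully comprehend and understand the consent form") may come before any arterial sample. Discomfort does not always end the procedure either, since Section 7.4 also provides for giving oxygen.

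**Share of valid pairs discarded**

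The figure of 22 cannot be reproduced because its inputs are redacted; it is taken as given. Every other input is an assumption: k subjects withdrawn, each having given a fraction f of a completer's pairs.

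s = k·f / (22 + k·f)

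| k | f = 0 | f = 0.25 | f = 0.5 | f = 1 |
|---|---|---|---|---|
| 1 | 0% | 0.25/22.25 = 1.1% | 0.5/22.5 = 2.2% | 1/23 = 4.3% |
| 3 | 0% | 0.75/22.75 = 3.3% | 1.5/23.5 = 6.4% | 3/25 = 12.0% |
| 5 | 0% | 1.25/23.25 = 5.4% | 2.5/24.5 = 10.2% | 5/27 = 18.5% |

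The last column is an upper bound, for subjects who stop after giving every pair a completer would give.

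**Effect on concordance from pair mix alone**

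Section 10 writes concordance as α·specificity + (1 − α)·sensitivity, where α is the share of pairs in the specificity denominator. If stoppers and completers have the same sensitivity and specificity but a different α, adding the stoppers moves concordance by

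s × (difference in α) × (specificity − sensitivity).

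At f = 0.5 with an assumed 10-point gap between specificity and sensitivity, for k = 1, 3, 5:

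- α differs by 0.2: 0.04, 0.13, 0.20 points
- α differs by 0.5: 0.11, 0.32, 0.51 points

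The shift can go either way, and a 5-point gap halves it.

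**Effect if stoppers perform differently**

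With completer concordance p and stopper concordance q, pooled concordance is (22p + k·f·q)/(22 + k·f). Take p = 0.95 as an assumption.

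| k | q = 0.7, f = 0.5 | q = 0.5, f = 1 |
|---|---|---|
| 1 | 21.25/22.5 = 0.944 | 21.4/23 = 0.930 |
| 3 | 21.95/23.5 = 0.934 | 22.4/25 = 0.896 |
| 5 | 22.65/24.5 = 0.924 | 23.4/27 = 0.867 |

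If q = p there is no shift, only lost pairs. Nothing in the documents supports a particular value of q.

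**The case against.** The strongest reply has five parts.

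- **The full protocol is undefined in the readable text.** The schedule grid is unreadable, and the readable step numbers jump from 7.4.11 to 7.4.17. The example of a stop in desaturation therefore rests on incomplete text. This stands as a limit on that example. It does not save the rule, because a stop within the oxygen steps loses pairs however the term is read.
- **Malfunction leaves nothing to analyse.** While the device cannot collect accurate optical data, there is no ORi to place in N1 to N4 under any analysis set. This is correct, and only pairs drawn before the malfunction are at issue. Wrong ORi readings in completers stay in the analysis.
- **The harm is not measured.** The pair-mix shift is small and assumes equal performance, while the larger shifts assume poor performance in stoppers. Both are illustrations only.
- **A completers-only set has a reason.** It keeps the range of PaO2 changes, and so α, comparable between subjects, and replacement keeps the planned precision. Both are fair points, and they are why the completers-only analysis should be retained.
- **Malfunctions are not hidden.** Deficiencies are reported under department procedures (Section 11, Adverse Events), device use is recorded per subject (12.2), and deviations are documented and reported (Section 16). None of these restores the pairs or puts the exclusions beside the performance results.

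**Conclusion.** The concern holds and should be fixed. Confidence is high that the Section 10 rule, read with 5.3.2, 5.4 and 9, makes inclusion depend partly on device function and discards valid pairs drawn before a stop. How much this matters cannot be determined from the documents, because they give neither the number of withdrawals nor their timing, and nothing on how the lost pairs perform.

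Under the assumed 1 to 5 withdrawals, the loss runs from nothing (all stop before sampling) to about 10% of valid pairs at half yield, and higher for later stops. Pair mix alone would move concordance by about half a point at most in the half-yield scenarios shown. A larger shift needs stoppers to perform differently from completers, which is possible but not shown.

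**What to change.** Replace the exclusion sentence in Section 10 with wording such as:

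> All valid paired PaO2/ORi samples are analysed from every subject who has a qualifying reference sample and at least one further sample with ΔPaO2 outside ±10 mmHg, including data collected before a stop, except where consent was not valid or the terms of consent do not allow the data to be used. A completers-only analysis is also reported.

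State in the same place what counts as a valid pair and what the full protocol comprises, so that both analysis sets are fixed in advance.

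Beside the performance results, report the number of subjects excluded or replaced, by reason, with device malfunction as its own category. Report blood draws with no usable ORi as a separate data-yield count that is not scored in N1 to N4. The withdrawal and replacement rules and the target of 22 completers stay as they are.

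The cost is a short change to Section 10, one extra analysis, a small table built from records already planned in 12.2 and Section 16, and IRB approval of the amendment. The drawback is that early stoppers may lack low-PaO2 samples and so shift α. The completers-only analysis and the separate sensitivity and specificity figures make that visible. Reported performance may move in either direction.

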2.2. Parameter Background

A continuous supply of oxygen is essential for normal cell function. Failure of a patient's oxygen supply to meet metabolic needs is common to all forms of circulatory failure, tissue acidosis, and ultimately mortality. Like all essential commodities for body functions, optimal quantities of oxygen are required. A patient's oxygen status can be largely classified into 3 ranges: Hypoxia (less than normal), Normoxia (normal) and Hyperoxia (more than normal). The three states are typically classified using dissolved oxygen levels in the plasma (PaO_2), instead of arterial hemoglobin oxygen saturation (SaO_2), due to sensitivity of PaO_2 in all three states including hyperoxia (unlike SaO_2). Figure I.¹ shows the three oxygen states based on PaO_2 values along with the relationship between PaO_2 and SpO_2 (which is a proxy for SaO_2)

OxyHemoglobin Dissociation Curve

[figure not shown]

Figure 1: The oxygen dissociation curve with the three oxygen states

¹ Martin, L. (1999). *All you really need to know to interpret arterial blood gases*, Page 73, Lippincott Williams & Wilkins.

Oxygen Reserve Index (ORi) Validation of INVSENSOR00014

In order to prevent episodes of hypoxia, patients in critical care are administered a certain amount of surplus oxygen to prevent hypoxia even when oxygen supply may be lost intermittently. However this excess supply should be in moderation as large amounts of oxygen may result in potential lung damage. Hence it becomes imperative to monitor the amount of surplus oxygen in blood.²

Currently, in order for clinicians to monitor a patient's oxygen status, both continuously and non-invasively, they utilize a pulse oximeter to obtain SpO₂ (a proxy for SaO₂) levels. However, SpO₂ is sensitive in the normoxic and hypoxic regions and largely remains flat in the hyperoxic region (Figure 1) clinicians generally resort to invasive blood draws to obtain PaO₂ values which provide oxygen status within the hyperoxic zone. This method has multiple drawbacks such as intermittent samples to potential delay between time of blood draw to the time when the PaO₂ value is obtained through blood gas machines.

The ORi Parameter may help provide clinicians with a convenient noninvasive method for reference information in regards to PaO₂. While not a direct measurement of PaO₂, ORi provides a continuous and non-invasive index which correlates with changes in PaO₂ values (in the range of 100 to 200mmHg).

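### Does scoring ORi against a threshold sample, and not in time order, leave the validation unable to do its job?

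*Combined protocol and SAP*

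**What the plan says.** Section 1 names the outcome: specificity, sensitivity and concordance of ORi against PaO2 from blood samples. Section 10 repeats it: "Specificity, sensitivity and concordance will be computed for changes in ORi with respect to changes in PaO2 as described below".

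The definition that follows is explicit. ΔPaO2 is the PaO2 at time t minus the PaO2 at t_ref, and t_ref "is the time of the sample closest to" the threshold, within a window of 10 mmHg either side. ΔORi uses the same two times. The threshold "can be any value from 110 to 190 in steps of 10mmHg (see footnote) to cover the range of 100 to 200mmHg", which makes nine thresholds. Samples whose ΔPaO2 lies within 10 mmHg are dropped. The counts N1 to N4 carry no index for time or leg.

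The samples come from a session with a rising and a falling phase. In Section 7.4, "Arterial blood samples will be drawn at specified targeted increments"; FiO2 "will be increased in specified targeted increments" and afterwards "will be decreased in specified targeted increments until reaching room air; samples should be drawn at each targeted saturation level". A desaturation phase follows.

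**The concern.** The word change suggests something that happens over time. Under Section 10 a positive change means only that PaO2 was higher than at the reference sample. The compared sample may have been drawn before the reference, or on the other leg. A reader could take the reported sensitivity as the device's ability to detect a rise or a fall as it occurs.

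Section 2.2 encourages that reading. It says that "ORi provides a continuous and non-invasive index which correlates with changes in PaO₂ values (in the range of 100 to 200mmHg"), and it explains that patients are "administered a certain amount of surplus oxygen to prevent hypoxia even when oxygen supply may be lost intermittently". Loss of supply is a fall over time. If ORi followed rises well and falls badly, the planned figures would not say so, although the design contains both legs. At stake would be a validation result that hides the weakness of most clinical interest.

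**Working it through.** **1. Does the score ignore time order?** Yes, from the definition. The reference depends only on PaO2 values, and N1 to N4 depend only on the signs of ΔPaO2 and ΔORi. Barring ties in choosing the reference, reordering a subject's samples changes nothing.

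**2. An exact example.** The draws are invented; the rules are those of Section 10. Rising PaO2 is 110, 130, 150, 170, 190 mmHg with ORi 0.10, 0.30, 0.50, 0.70, 0.90. Falling PaO2 is 188, 168, 148, 128, 108 with ORi 0.45, 0.55, 0.40, 0.60, 0.30. The falling leg is poor.

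At threshold 150 the reference is the draw at 150 (ORi 0.50). The reference itself and the draw at 148 are dropped.
- Higher PaO2: 170, 190 and 168 agree; 188 (ORi 0.45) does not. Score 3/4.
- Lower PaO2: 110, 130 and 108 agree; 128 (ORi 0.60) does not. Score 3/4.
- Concordance: (3 + 3)/8 = 6/8.

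Section 10 does not say whether thresholds are pooled. Pooling is assumed here:

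| Threshold | Reference PaO2 | Higher | Lower |
|---|---|---|---|
| 110 | 110 | 8/8 | 0/0 |
| 120 | 128 | 2/6 | 2/2 |
| 130 | 130 | 6/6 | 1/2 |
| 140 | 148 | 4/4 | 3/4 |
| 150 | 150 | 3/4 | 3/4 |
| 160 | 168 | 1/2 | 5/6 |
| 170 | 170 | 1/2 | 6/6 |
| 180 | 188 | 0/0 | 4/8 |
| 190 | 190 | 0/0 | 8/8 |
| All | | 25/32 | 32/40 |

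Concordance is (25 + 32)/72 = 57/72, or 79%. Run the session backwards, so that the rising leg is the poor one, and every entry is the same. Within leg and in time order, the first session gives rises 10/10 and falls 6/10; the reversed one gives rises 6/10 and falls 10/10. The loss of attribution is real.

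**3. Does the score still see the fault?** Yes. If ORi rose strictly with PaO2 on both legs, every sign would agree and the score would be 72/72. One poor leg brings it to 57/72. A simulation agrees. It assumed 22 subjects, 8 draws per leg, ORi linear in PaO2, noise SD 0.03, and extra noise SD 0.30 on the weak leg. Concordance was 0.999 for a sound sensor and 0.862 with either leg weak.

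**4. Is the information lost?** No. Section 7.4.3 records ORi with data-collection software, and draws are made on both legs. Keeping the planned reference and sorting the 72 comparisons by the leg of the compared sample already gives 33/36 on the rising leg and 24/36 on the falling leg. The reversed session gives the mirror image. Nothing in the plan prevents such a table.

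**5. Would a within-leg score be better?** It answers another question and has blind spots of its own. In the simulation of step 3, with a constant ORi offset of 0.25 on the falling leg in place of the extra noise, each leg scored 0.999 while the planned concordance fell to 0.906. In a separate simulation with assumed carry-over of 30, 50 and 70%, planned concordance was 96.7, 88.9 and 77.0%, while within-leg agreement stayed between 94.8 and 99.5%. Pooling across legs is what makes the planned score sensitive to these faults.

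**6. Would counting each pair (t, t_ref) once matter?** Not in the example. Nine of the ten draws serve once as reference, with 8 comparisons each: 9 × 8 = 72 distinct ordered pairs, so nothing is removed. Ignoring order there are 45 − 5 = 40 pairs, since five pairs lie within 10 mmHg, so mirror-image comparisons would remain. Across the simulated schedules the rule moved concordance by at most 0.3 points.

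**The case for a change.** The strongest case for the concern is that two opposite faults give identical results to the last count, and this needs no simulation. Sensitivity and specificity do not rescue it: they separate samples on either side of the reference, not rising from falling periods, and a weak leg lowers both about equally. The legs exist in the design, a by-leg line needs no extra draws, and it is most credible if fixed before the data are seen.

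The arithmetic stands, and so does the caution in reading: the planned figures describe how ORi orders samples around a reference, not how quickly or in which direction it responds. But Section 10 defines exactly that, so a label calling it ordering would only restate the definition. The sentence in Section 2.2 about lost supply explains why patients are given surplus oxygen; it sets no performance claim for ORi. The other sentence claims correlation with changes in PaO2 between 100 and 200 mmHg, which a threshold comparison over that range addresses.

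A by-leg supplement would also need choices of its own, such as where the peak and desaturation samples belong. With a mild one-leg fault it would show little: over the simulated schedules the within-leg gap at noise SD 0.10 was 0.1 to 4.5 points.

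**Conclusion.** The concern does not hold. The planned measures are independent of time order and cannot attribute errors to a leg, but they are the stated outcome, computed by an explicit rule, and they fall when either leg is poor (72/72 to 57/72 in the example; 0.999 to 0.862 in simulation). The effect on the validity of the planned estimates is nil: no bias, no unmet objective and no changed pass or fail result can be shown. A breakdown by leg is an optional extra from data the study already collects.

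That the counts ignore order follows from the formula alone. The sizes rest on assumed draws, noise and carry-over, and on pooling the thresholds. The published text gives none of these, and Figure 2 is not shown, so no assumption is made about which measure belongs to the higher side. The judgement would differ only if the plan claimed separate detection of rises and falls over time, which the documents do not do.
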